8.0 ADVERSE EVENT REPORTING

Adverse events are reported using two case report forms: Adverse Event and Serious Adverse Event. Adverse events will be collected starting at the time the patient is randomized and throughout the study, including during the hospital stay, any follow up visits and during any unscheduled patient contact or visits. The definitions and details are provided in the following sections.

Data Collection Requirements

Adverse Event Type	Adverse Event Form	Serious Adverse Event Form
Non-Serious Adverse Event	Complete entire form	DO NOT COMPLETE
Serious Adverse Event	DO NOT COMPLETE	Complete entire form

8.1. Anticipated Adverse Events

There are immediate post-operative events that are changes from the baseline condition of the Subject, but are expected events resulting from the surgery. If these events occur, they should be recorded in the Subject's medical record and reported forward as AEs to the study sponsor.

8.2 Adverse Events

An adverse event (AE) is any untoward medical occurrence, unintended disease or injury, or untoward clinical signs (including abnormal laboratory findings) in subjects, users or other persons, whether or not related to the investigational medical device.

At each evaluation of the subject enrolled in a clinical investigation, the investigator determines whether any adverse events (AE) have occurred, and determines their relationship to the study devices or procedure.

All adverse events, study device malfunctions and other product issues must be recorded in the medical records and entered into CRFs.

8.3 Serious Adverse Events

Serious Adverse Events (SAEs) are defined as any adverse event that:

a) led to death,

b) led to serious deterioration in the health of the subject, that either resulted in

- 1) a life-threatening illness or injury, or
- 2) a permanent impairment of a body structure or a body function, or
- 3) in-patient or prolonged hospitalization, or

4) medical or surgical intervention to prevent life-threatening illness or injury or permanent

impairment to a body structure or a body function,

c) led to foetal distress, foetal death or a congenital abnormality or birth defect

NOTE Planned hospitalization for a pre-existing condition, or a procedure required by the CIP, without serious deterioration in health, is not considered a serious adverse event.

The investigator must submit to sponsor and CFDA (or designee) any Unanticipated Adverse Device Effects (UADE) and SAEs occurring during the study within 24 hours after being notified of the event and provide additional information if required by sponsor.

All SAEs need to be followed until the event is resolved (with or without sequelae). The medical monitor of this study will decide if more follow-up information is needed in case the event is not resolved or stable at study completion.

The investigator notifies his/her EC of all SAEs and UADEs occurred at his/her site (and any additional information as required by Ethics Committee). The investigator notifies competent authority of all SAEs and UADEs that occurred at his/her site in accordance with local regulation requirements.

The sponsor will report to all participating clinical investigators all UADEs and deaths within 5 working days after the sponsor first receives notice of the effect and/or event. The sponsor will submit every year (unless otherwise indicated by the Ethics Committee or recommended by the local regulations to all participating clinical investigators an update of all study devices related, site reported and adjudicated SAEs. A letter summarizing the study status, enrollment figures, any safety concerns as well as any recommendation from the steering committee will accompany the updates.

Event reporting to relevant competent authorities will occur by the sponsor in a manner and timing in accordance with local regulation requirements.

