13.1. Investigational Device Accountability 13.2. Return of Study Devices	
13.3. Device Complaint	
APPENDIX A: Definitions	
APPENDIX B: Referenced Published Literature and Joint Registries	51
APPENDIX C: Device Part codes and Specifications – TFNA	53
APPENDIX D: DEVICE PART CODES AND SPECIFICATIONS - PFNA-II	64
APPENDIX E: ABBREVIATIONS	73

	Synopsis
Study Title	A Prospective Study Evaluating Trochanteric Fixation Nail Advanced (TFNA) in a Chinese Patient Population
Study objective:	The primary objective of this study is to evaluate whether fracture union rate, evaluated 24 weeks after proximal femur fracture, for the investigational TFNA intramedullary nail is non-inferior to that for currently available control product PFNA-II in patients with proximal femur fractures.
Country	China
No. of clinical sites	Up to 15
No. of Patients	188 patients enrolled
Duration of subject participation	Enrollment of 188 subjects is anticipated to require approximately 8-10 months. Each subject will undergo six months of clinical and radiographic follow-up. Total study duration is approximately 16 months.
Study Design	The Trochanteric Fixation Nail Advanced (TFNA) is an implant designed to treat proximal femur fractures and is currently in use in several regions worldwide (e.g., US, Europe). TFNA is manufactured using a titanium-molybdenum alloy (TiMo) that has not been used for a similar clinical application within China. The purpose of this study is to evaluate TFNA to support registration of the product in China. The study is a prospective, multicenter, controlled, two-arm, randomized, non-inferiority study comparing the 24-week fracture union rate for proximal femur fractures treated with intramedullary nails using investigational devices (TFNA) compared to control devices (Proximal Femoral Nail Antirotation, PFNA-II), under a 10% non-inferiority margin. The study population will include 188 patients with proximal femur fracture undergoing internal fixation using an intramedullary nail. Subjects will be randomized in a 1:1 ratio to receive either the investigational TFNA devices (n=94) or to the control PFNA-II
	devices (n=94). The primary endpoint (fracture union) will be assessed by clinical and radiographic follow-up at 24 weeks. An independent reviewer will evaluate radiographs for evidence of fracture healing and implant integrity. Secondary endpoints will include safety and efficacy outcomes, radiographic outcomes and adverse events.

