10.11. Plans for Interim Analysis

No interim analysis is planned for this study for the purpose of stopping the study early.

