EuroQoL (Quality of Life)-5 Dimensions (EQ5D): The EQ5D is a patient reported outcome. It provides a simple descriptive profile and single index value for health status. This health-related, quality of life survey consists of five dimensions (mobility, self-care, usual activities, pain/discomfort, anxiety/depression) each of which can take one of five responses. The responses record five levels of severity (no problems/slight problems/moderate problems/severe problems/extreme problems) within a particular EQ-5D dimension.

PROTOCOL DEVIATION

A protocol deviation is defined as an incident where the Investigator or site personnel did not conduct the study according to the investigational plan, protocol or the Investigator agreement.

Major deviation: Any deviation from patient inclusion and exclusion criteria or patient informed consent procedures.

Minor deviation: Deviation from a protocol requirement such as incomplete/inadequate patient testing procedures, follow-ups performed outside specified time windows, etc.

SERIOUS ADVERSE EVENT

A Serious Adverse Event (SAE) is any untoward event that:

a) led to death,

- b) led to serious deterioration in the health of the subject, that either resulted in
- 1) a life-threatening illness or injury, or
- 2) a permanent impairment of a body structure or a body function, or
- 3) in-patient or prolonged hospitalization, or
- 4) medical or surgical intervention to prevent life-threatening illness or injury or permanent impairment to a body structure or a body function,
- c) led to foetal distress, foetal death or a congenital abnormality or birth defect

NOTE Planned hospitalization for a pre-existing condition, or a procedure required by the

CIP, without serious deterioration in health, is not considered a serious adverse event.

UNANTICIPATED ADVERSE DEVICE EFFECT (UADE)

An Unanticipated Adverse Device Effect (UADE) is defined as any serious adverse effect on health or safety or any life-threatening problem or death caused by, or associated with, a device, if that effect, problem, or death was not previously identified in nature, severity, or degree of incidence in the investigational plan or application (including a supplementary plan or application), or any other unanticipated serious problem associated with a device that relates to the rights, safety, or welfare of subjects.

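### On the planned timeline, the default yearly update of non-fatal, non-UADE device-related SAEs first reaches investigators after the last planned implantation

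*Protocol*

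**What the plan says.** Protocol section 8.3 sets two routes from the sponsor to the sites.

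- **Expedited:** "The sponsor will report to all participating clinical investigators all UADEs and deaths within 5 working days" of the sponsor receiving notice.
- **Periodic:** "The sponsor will submit every year (unless otherwise indicated by the Ethics Committee". The same exception covers a different interval under local rules. What is sent is a summary of the device-related SAEs, both as the sites reported them and as adjudicated. A letter goes with it, giving study status, enrolment figures, safety concerns and any steering committee recommendation. Yearly is therefore a default that an ethics committee or local rule can change. The section does not say when the year starts.

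Appendix A decides which route a serious device-associated event takes. It is a UADE "if that effect, problem, or death was not previously identified in nature, severity, or degree of incidence in the investigational plan".

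On timing, the Synopsis says: "Enrollment of 188 subjects is anticipated to require approximately 8-10 months". It adds six months of follow-up per subject and a total of about 16 months, but also gives a study period of 2018-2021. Section 10.11 states: "No interim analysis is planned for this study for the purpose of stopping the study early".

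**The concern.** A periodic safety update protects subjects only if it arrives while some are still to be treated. Here the default interval is longer than the planned enrolment.

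The events affected are the ones most likely to distinguish two nails of similar design. Cut-out, implant breakage, migration, nonunion, later femur fracture and infection are already named between section 2.2 and Tables 2 and 4, so they are not UADEs by nature. They could qualify by incidence, but judging that needs a running count by device with the number implanted, and the protocol schedules none.

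TFNA uses an alloy new to this application in China. If a known failure mode were more frequent with it, each site would see only its own few cases. The letter meant to give investigators the wider picture would come too late to affect any implantation.

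**Working it through.** **Inputs.** From the Synopsis: enrolment about 8-10 months, follow-up 6 months, total about 16 months, up to 15 sites. From section 10.9: 94 per group, 188 in total. From section 8.3: a default interval of 12 months. Assumptions: the year runs from first enrolment, implantation closely follows enrolment, and accrual is uniform.

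**1. The plan's own figures.**
- Duration: 8 + 6 = 14 months and 10 + 6 = 16 months. The upper end matches the stated 16.
- Sample size: 95% union in both groups, a 10% margin, one-sided 2.5% alpha and 80% power give 75 per group. 75 / 0.80 = 93.75, rounded up to 94, so 188. Both figures reproduce.

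**2. When the default update arrives.**
- Gap after enrolment closes: 12 − 10 = 2 months to 12 − 8 = 4 months.
- Yearly updates within 16 months: 16 / 12 = 1.33, so one.
- Planned subjects implanted by month 12: 188 of 188.

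**3. How far this depends on the assumptions.** The number implanted at month 12 is 188 × min(1, 12/E) for an enrolment of E months:

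| Enrolment E (months) | Implanted at month 12 | Still to implant |
|---|---|---|
| 8, 10 or 12 | 188 | 0 |
| 14 | 161 | 27 |
| 18 | 125 | 63 |
| 24 | 94 | 94 |

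Enrolment must exceed 12 months before a yearly update reaches sites during implantation. If the year instead started s months before first enrolment, the update would fall within enrolment only when s exceeds 12 − E, that is 2 months (E = 10) to 4 months (E = 8).

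**4. What a 3-monthly update would reach.** Implanted at month t: 188 × t / E.
- Month 3: 188 × 3/10 = 56 to 188 × 3/8 = 70.5, leaving about 118 to 132.
- Month 6: 188 × 6/10 = 113 to 188 × 6/8 = 141, leaving 47 to 75.
- Last visit at months 14-16: 14/3 = 4.7 and 16/3 = 5.3, so four or five updates in all, one of them the existing month-12 update.

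**5. What one site can see.** I use a cut-out rate of 7.5%, the top of the Table 2 range.
- 15 sites: 188/15 = 12.5 subjects, 6.3 per arm; 6.3 × 0.075 = 0.47 expected cut-outs per arm.
- The 10 sites in SAP Tables 4-13: 18.8 subjects, 9.4 per arm; 9.4 × 0.075 = 0.7.

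A typical site would therefore expect less than one such event per arm.

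**The case against.** A reader might infer that all device-related SAEs reach investigators only once a year. The documents do not support that. UADEs and deaths go to all investigators within 5 working days, and the UADE definition covers effects that are unexpected in severity or incidence as well as in nature.

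A reader might also infer that safety is unwatched during enrolment, so that the suspension power in section 9.3 has nothing to act on. That is not supported either. The power belongs to the sponsor, which under section 8.3 receives every SAE within 24 hours. Section 8.3 also names a medical monitor and a steering committee. Under section 10.10.3 the data are reviewed as they are collected, and no passage blinds the sponsor. Section 11.1.2 adds a general duty to tell investigators and ethics committees of relevant safety issues, so it cannot be said that they would receive no pooled information. These points stand. What they do not provide is a second scheduled route to the other sites.

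Two further objections bear on the remedy.

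- **By-arm counts sent to investigators would not be harmless.** Radiographic union and an intact implant are components of the primary endpoint (section 5.1). Investigators are not blinded (section 7.5), and local examination is part of the visit schedule. Regular by-arm tallies of nonunion and breakage could influence assessment. Many Table 2 and 4 items also need not be serious, and non-serious events carry no 24-hour report. This stands and shapes the fix.
- **Three months is not derived from a detection target.** At month 3 there would be 28-35 subjects per arm, and at 7.5% about 2.1-2.6 cut-outs per arm (28.2 × 0.075; 35.25 × 0.075), too few to separate the devices. Table 2 ranges reaching 22.6% for fixation failure and 47.1% for reoperation are weak benchmarks. This also stands: an earlier update gives timely information and is not a test. It does not justify an interval longer than enrolment.

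**Conclusion.** The point holds for non-fatal device-related SAEs that are not UADEs. For these, the yearly update is the only scheduled cross-site route. On the planned 8-10 month enrolment it would first arrive at month 12, 2-4 months after enrolment closes and after all 188 planned implantations.

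This rests on three conditions: the default interval is not changed by an ethics committee or local regulation, the year runs from first enrolment, and enrolment keeps to plan. None is certain. The enrolment time is approximate, the start of the year is undefined, and the 2018-2021 study period is not reconciled with 16 months. Slower accrual weakens the point, but even with a 14-month enrolment about 161 of 188 subjects would be implanted before the first update.

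The gap is in circulating pooled information to sites. Case reporting to the sponsor is prompt. The change is a cheap improvement to subject safety and leaves the primary analysis untouched.

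**What to change.** In protocol section 8.3:

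1. Replace the yearly default with an interval that falls within enrolment and has a stated start, for example every 3 months from first implantation until the last 24-week visit. Keep the exception for ethics committees and local regulations.
2. Keep the existing content (device-related, site-reported and adjudicated SAEs plus the status letter) and add the number implanted to date.
3. Give the medical monitor, and ethics committees on request, cumulative SAE counts by device received with the number implanted, so that the incidence part of the UADE definition can be applied.
4. Send investigators counts pooled over devices plus any stated safety concern, without by-arm tallies of nonunion or implant breakage.

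The cost is one amended passage and four or five short tabulations in place of one, drawn from SAE reports that the sponsor already receives within 24 hours. Endpoint, sample size and alpha do not change.

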8.4. Duration of Follow-up after Adverse Events

The Investigator should ensure that adequate medical care is provided to any subject for any adverse events, including clinically significant laboratory values, related to the study.

All adverse events related to the subject's participation in the study should be followed until the condition has resolved, or in the case of permanent impairment until the condition stabilizes and clinical outcome has been ascertained.

8.5. Reporting an Adverse Event

Adverse events are reported from the start time of the index procedure until the subject's study participation has ended (i.e. revision, completion of study or withdrawal of consent). All AEs must be followed until the AE has resolved, stabilized, or the study has been completed.

The Investigator will record the nature, severity, treatment and outcome of the AE, and will

determine the relationship to the investigational products, medications or any protocol mandated procedures involved in the clinical study.

The following categories of adverse event severity are to be used:

Mild:	Awareness of sign or symptom that does not interfere with the subject's
	usual activity or is transient, resolved without treatment and with no
	sequelae,
Moderate:	Interferes, but does not hinder, the subject's usual activity and may
	require treatment,
Severe	Symptom(s) causing severe discomfort and significant impact on the
	subject's usual activity and requires treatment or intervention.

The causal relationship should be rated as follows:

Unrelated:	The event is definitely not associated with product application
Unlikely:	The temporal sequence between product application and the event is such that the relationship is unlikely,
Possible:	The temporal sequence between product application and the event is such that the relationship is not unlikely or the subject's condition or concomitant therapy could have caused the AE,
Probable:	The temporal sequence is relevant or the event abates upon product application completion or the event cannot be reasonably explained by the patient's condition,
Related:	The temporal sequence is relevant and the event abates upon product application completion or reappearance of the event on repeat product application (re-challenge).

Adverse events will be reported by the investigator to the Sponsor via the CRF.

9.0 EARLY DISCONTINUATION

9.1 Reasons for Early Discontinuation

Possible reasons for early discontinuation may include, but are not limited to the following:

- Withdrawal of consent: Subject decides to withdraw from the study. This decision must be an "independent decision" that is documented in the patient study files;
- Physician discretion: The Investigator may choose to withdraw a subject from the

study if there are safety concerns;

- Adverse event: Adverse event or serious adverse event may not lead to subject discontinuation from the study. When the investigator decided to discontinue the subject, subject must be followed until the adverse event resolves or until a stable clinical endpoint is reached;
- Death;
- Early study termination: The sponsor can decide to discontinue the study prematurely for various reasons.
- Lost to follow-up: All subjects should be encouraged to return for all scheduled clinical follow-ups, and to provide appropriate contact information to accommodate completion of required telephone follow-ups. If a subject is unable to return for mandatory clinical visits, 3 separate telephone calls should be made to attempt to bring the subject back into the clinic and/or obtain safety information and assess implant status. All attempts at contact should be documented in the source documents. If the subject does not respond to 3 telephone calls, the Investigator must send a registered letter to the subject. If the subject does not respond to the registered letter and further contact is not made, then the subject will be considered to have missed the scheduled visit. If the aforementioned contact efforts are unsuccessful over two study intervals the subject will be considered lost to follow-up and an End of Study case report form (CRF 9) must be completed.

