7.5. Blinding Procedures

Many medical records (source documents) documenting the patient's operative procedure, hospital stay and follow-up visits will not be blinded because implant labels identifying the implanted stems will be provided. As is common in device trials, it will not be possible to blind surgeon investigators or study staff because each group will be implanted with a different implant system, each of which is easily distinguished and has its own instrument set. Blinding of the independent radiographic reviewers and study staff also is not feasible because of small differences in design features that may be distinguished postoperatively (e.g., radiographs).

Blinding practices for this study will include the following:

Patients: Patients will be informed of the 1:1 randomization between the two devices, but will remain blinded as to which implant they actually received until after they have completed all study follow-up.

Implanting surgeon: It is not possible to blind the implanting physician due to his/her contact with the product labeling and IFU.

Independent Radiographic Reviewer (IRR): The IRR will not be blinded to the device implanted due to small differences that may be apparent in the radiographic images.

Medical Records: All medical records (source documents) documenting the implant procedure through hospital discharge and all follow-ups will not be blinded because implant labels identifying the implanted stems will be provided.

Monitors: Monitors will not be blinded because the detachable labels provided with the product identify the product and may be used in the study device accountability records and patient research file for the purpose of device accountability and source document validation.

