9.2. Subject Early Discontinuation

Every subject should be encouraged to remain in the study until they have completed the protocol-required 24-week follow-up period. If the subject discontinues prematurely from the study, the reason for discontinuation must be documented in the source documents and site files, and submitted via CRF.

Subjects who have discontinued prematurely will be included in the analysis of results; however new subjects may not be enrolled to replace these subjects.

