6.4 Detailed rules for determination of analysis population set and flow chart

- (1) No investigational device is implanted: Subjects obtain random numbers but do not use any study-related treatment (implantation study group, control group or third party products);
- (2) Violation of inclusion and exclusion criteria: The subjects do not meet the inclusion criteria or meet the exclusion criteria set in the study protocol, and the violation of this protocol will seriously affect the results of primary efficacy endpoints; the sponsor, investigators and statisticians will jointly determine through a blind review meeting whether the protocol violation will seriously affect the results of primary efficacy endpoints;
- (3) Loss to follow-up during the trial: Subjects are unable to obtain the fracture union rate 24 weeks after the primary endpoint surgery;
- (4) Cross enrollment: Subjects randomly assigned to the study group receive the control products, while subjects randomly assigned to the control group receive the investigational products;
- (5) Out-of-window time: The difference between the follow-up date at 24 weeks after primary endpoint surgery and the surgery date do not fall within the range of [140, 196], and the violation of this protocol may seriously affect the results of primary efficacy endpoints; the sponsor, investigators and statisticians will jointly determine through a blind review meeting whether the protocol violation will seriously affect the results of primary efficacy endpoints;
- (6) Out-of-specification use of investigational products: The specifications of the device implanted in the subject are not within the specification range specified in the study protocol;
- (7) Use of third party products: The subjects randomly assigned to the study group or the control group use third party products;

(8) FAS = Number of subjects enrolled in the trial - Number of subjects not implanted with any investigational device;

PPS = FAS - Number of subjects who seriously violate the study protocol;

ATS = PPS + Number of cross-enrolled subjects alone; ATS will be displayed if subjects are cross-enrolled in the trial, while ATS will not be displayed if no cross-enrollment occurs.

Number of subjects who seriously violate the study protocol = Violation of inclusion and exclusion criteria + Loss to follow-up during the trial + Cross enrollment + Out-of-window time + Out-of-specification use of investigational products + Use of third party products;

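### Protocol 9.1 lets a subject be closed out before the week-24 window opens, and nothing in the plan then calls for the week-24 outcome to be obtained

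*Protocol*

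**What the plan says.** Protocol 9.1 gives two routes by which a subject can leave before week 24 without dying or withdrawing consent.

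- **Failed contact.** Three telephone calls come first, then: "If the subject does not respond to 3 telephone calls, the Investigator must send a registered letter to the subject". If that also fails, the visit counts as missed. When these efforts "are unsuccessful over two study intervals the subject will be considered lost to follow-up and an End of Study case report form" must be completed. The rule does not say that one of the two intervals has to be week 24.
- **Investigator withdrawal.** The physician-discretion bullet reads "The Investigator may choose to withdraw a subject from the" study where there are safety concerns, and sets no follow-up. The adverse-event bullet says "Adverse event or serious adverse event may not lead to subject discontinuation from the study". It then covers the case where the investigator does discontinue: "subject must be followed until the adverse event resolves or until a stable clinical endpoint is reached".

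Protocol 9.2 adds a general aim: "Every subject should be encouraged to remain in the study until they have completed the protocol-required 24-week follow-up period". It also says that early discontinuers will be included in the analysis. Neither document provides for a week-24 examination or film after close-out.

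On the analysis side, SAP 6.4(3) treats as lost anyone for whom this applies: "Subjects are unable to obtain the fracture union rate 24 weeks after the primary endpoint surgery". Such subjects are removed from the PPS.

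**The concern.** Union is judged at one visit. A subject closed before that visit's window opens has no primary outcome, although the implant is still in place and the subject may still be willing or able to be seen. Leaving the study ends observation, not exposure.

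The safety route matters most. The person deciding knows the arm (Protocol 7.5: "it will not be possible to blind surgeon investigators or study staff"), and subjects withdrawn over safety are selected on a poor course. If failures go unseen in the TFNA arm, the observed difference moves towards the non-inferiority claim. If they go unseen in the control arm, it moves the other way. Either way the loss is partly avoidable.

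**Working it through.** **1. The plan's own sample size.** Inputs (Protocol 10.9, Synopsis): union 95% in both arms, margin 0.10, one-sided 0.025, power 80%, attrition 20%.

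n = (1.960 + 0.842)² × 2 × 0.95 × 0.05 / 0.10² = 7.85 × 0.095 / 0.01 = 74.6, so 75 per arm. Then 75 / 0.80 = 93.75, so 94 per arm and 188 in total. The stated figures reproduce, and this point does not affect them.

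**2. When close-out can happen.** Windows (Protocol 10.4; SAP 6.4(5) for week 24):

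- week 1: days 1 to 14
- week 6 ± 2 weeks: days 28 to 56
- week 12 ± 2 weeks: days 70 to 98
- week 24 ± 4 weeks: days 140 to 196

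The protocol names no close-out day, so the window ends are used:

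- contact fails at weeks 1 and 6: from day 56, which is 140 − 56 = 84 days before the week-24 window opens
- contact fails at weeks 6 and 12: from day 98, which is 140 − 98 = 42 days before
- contact fails at weeks 12 and 24: not closed before the window, so no issue

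Investigator withdrawal has no fixed timing.

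**3. Where these subjects go in the primary analysis.**

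- Protocol 10.8 and 10.10.5: the Per Protocol set requires 24 weeks of follow-up and a known outcome, so they are out.
- SAP 7.3: one missing component makes the composite missing. SAP 6.4 then removes the subject from the PPS, and the ATS is built on the PPS.
- SAP Table 30, first block (FAS): missing outcomes are left unprocessed, so they are out.
- Protocol 10.5: LOCF is run on the Per Protocol set, which has already excluded them.
- SAP 6.5 and Table 30, second block (FAS with LOCF): they are in, scored as non-union unless union was definite.

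Only the last reaches them. A subject closed after weeks 6 and 12 has nothing later than week 1, and the SAP's week-1 film table (Table 58) has no union determination. LOCF then supplies a rule, not information.

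**4. Size, as an illustration.** The plan allows 94 − 75 = 19 missing per arm. Among 75 observed at 95% union there are 71.25 successes and 3.75 failures. Suppose k of the missing subjects in one arm would have been failures had they been seen. That arm's rate becomes 71.25 / (75 + k):

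- k = 1: 71.25/76 = 93.75%, a shift of about 1.3 points
- k = 3: 71.25/78 = 91.3%, about 3.7 points
- k = 5: 71.25/80 = 89.1%, about 5.9 points

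k is an assumption; the documents give no number of early close-outs or safety withdrawals. Equal losses in both arms would largely cancel in the difference.

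**5. Precision.** Power = Φ(0.10 / √(2 × 0.95 × 0.05 / n) − 1.960). At n = 75 it is 80.2%; at n = 94 it is 88.2%. The second figure is a ceiling, since deaths and withdrawn consent cannot be retrieved.

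**The case against.** The case against is substantial and mostly limits the claim.

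- **Close-out is not triggered by missed visits alone.** Three calls and a registered letter must fail in each of two intervals. A subject who skips visits but answers the telephone stays in. Day 56 is the earliest case, not the typical one. This stands.
- **A reader might infer that the losses fall mostly on problem cases.** The documents do not support that: they give no frequencies or reasons, and nothing ties loss of contact to non-union. Selection on a poor course is inherent only in the safety route.
- **A reader might infer that the outcome is forbidden after close-out.** It is not. Protocol 9.1 requires a form and does not bar a later visit. The gap is that no visit is required.
- **The adverse-event bullet could be read as contradicting itself.** It can equally mean that an event need not lead to discontinuation. It is ambiguous rather than wrong.
- **The two uses of loss to follow-up could be read as a conflict.** Protocol 9.1 is an operational close-out rule and SAP 6.4(3) labels an analysis set. They do different jobs, so the difference is not an error.
- **The LOCF analysis in the FAS counts most such subjects as failures.** That partly offsets the loss, but only as a sensitivity analysis.
- **The 19 missing per arm is total attrition.** Protocol 10.9 refers the 20% to Section 1.3, which reports one-year mortality of 0% to 24%. Some of that loss cannot be recovered by any rule.

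None of this supplies a week-24 attempt where one could still be made.

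**Conclusion.** The point holds as a cheap improvement. Protocol 9.1 permits close-out before day 140 by two routes and the plan makes no provision to obtain the week-24 outcome afterwards. The affected subjects are absent from every primary-endpoint estimate except the SAP's LOCF analysis in the FAS. The missingness may be informative, particularly where an unblinded investigator withdraws a subject over safety.

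The size is not known from the documents. The range of about 1.3 to 5.9 points rests on three assumptions: 1 to 5 unseen subjects, all of them failures, all in one arm. It shows what a few cases could do to a 10-point margin and is not an estimate of bias. It would be too strong to conclude that the primary result will be biased, or that most early losses are failures.

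**What to change.** Amend Protocol 9.1 and 9.2:

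1. Do not complete the End of Study form for loss to follow-up before day 196.
2. For every implanted subject who is alive and has not withdrawn consent, carry out the full contact sequence for the week-24 examination and films, whatever earlier visits were missed.
3. State that investigator discontinuation for an adverse event or safety concern does not by itself end collection of adverse events and the week-24 union assessment. The investigator may still omit any study procedure judged unsafe for that subject.
4. Reconcile the two sentences of the adverse-event bullet so that only one reading is possible.

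No new visit or assessor is needed, and the sample size is unchanged. The cost is some extra calls and letters, and CRFs that stay open to day 196. Some subjects will remain unreachable, so the LOCF analysis in the FAS is still needed.
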